The primary study aim is to conduct a pilot randomized controlled trial (RCT) to (1) assess feasibility, acceptability, and fidelity of SBI-HV, and (2) determine the preliminary impacts of SBI-HV on client symptom reduction (SU, depression, parenting stress), retention in HV, engagement in SU treatment, and alliance between the home visitor and client. The pilot RCT will be conducted in New Jersey, in counties that are implementing the Healthy Families America (HFA) home visiting program. We will enroll 20 home visitors and 40 clients. The pilot RCT will be a cluster-randomized trial, with home visitors randomly assigned to study condition. Feasibility, acceptability, and fidelity will be assessed via home visitor and client interviews and fidelity checklists. Clients will be assessed at baseline, and 3- and 6-month follow-up to track SBI-HV impacts on outcomes.

STUDY PARTICIPANTS

The study will be conducted within New Jersey (NJ)'s HV system within the Healthy Families America (HFA) HV program. Participation will be offered to all HFA home visitors throughout the state

Home Visitors

We will enroll 20 HFA home visitors in the trial. Based on our prior research with this population, we expect the home visitors to have the following demographic characteristics: 100% female, average age 36 years, 25% White, 40% Latina, 30% Black, average 5 years HV experience, and 60% with greater than a high school education.

Clients

We will enroll 40 clients who meet the following study eligibility criteria: (1) speak English or Spanish; (2) age 18 years old or older; (3) pregnant or up to 3 months postpartum; (4) enrolled in HFA with a participating home visitor within the prior six months; (5) reporting binge drinking or illicit drug use in the 3 months prior to their most recent pregnancy and not currently attending substance use treatment; and (6) have access to smartphone or other internet-enabled device with internet connection. Based on prior work with this population, we expect clients to have the following demographic characteristics: 40% Latina, 41% White, 34% Black,

63% single, 22% with a high school education or less, 78% unemployed, 85% on public assistance, and 15% child welfare system-involved.

STUDY CONDITIONS AND HV-SBI COMPONENTS FOR EACH CONDITION

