Qualitative feasibility interviews (approx. 30 minutes) will be conducted via zoom with all home visitors and a random sample of 10 clients (balancing on pregnancy status) in the intervention condition during the second half of the pilot RCT to assess feasibility and acceptability of the SBI-HV. We will randomly select 10 clients to participate in the interview. Selection will be random with one exception: we will ensure that the proportion of pregnant women in the interview sample of 10 is representative of the proportion of pregnant women in the overall sample. Thus, if the overall sample of 20 women in the experimental condition includes 8 pregnant women, we will randomly select 6 non-pregnant women and 4 pregnant women to participate in the interviews. All interviews will be one-on-one. Clients and home visitors will be interviewed separately. All qualitative interviews will be recorded and transcribed, in accordance with gold standard procedures for collection and analysis of qualitative interview data. While we prefer that clients and home visitors have their video cameras on during the interview to allow for a more natural conversation, clients and home visitors will have the option to leave their cameras off and join with audio only if they are more comfortable with that. Recordings of qualitative interviews will include audio only, using the setting on Zoom that allows for recording of audio only without video. Thus, no recordings will include video. If a participant is not comfortable being recorded, they can still participate in the interview; the interviewer will take detailed notes on what is said. Clients will also complete a series of quantitative rating scales at the end of each e-SBI session assessing user satisfaction. Home visitor fidelity will be assessed via brief questions delivered via text message following virtual visits in which facilitation protocols are intended to be implemented. Home visitors will also be asked to complete a brief Qualtrics survey prior to SBI-HV training to assess demographics and readiness to implement evidence-based interventions.

Outcome Data Collection

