SBI-HV Impacts on Client Outcomes. The study will use a randomized intent-to-treat design, with home visitors randomly assigned to condition (routine HV vs. HV+SBI-HV). Data will have a 3-level nested structure: clients (N=40) within home visitors (N=10-20) within sites. Given the small number of home visitors and sites, modeling each as a random effect would not yield stable estimates. Therefore, we will use the sandwich variance estimator to adjust standard errors as appropriate to account for nesting of clients within home visitors. Site will be included as a fixed covariate in all models. We will conduct ANOVA or chi-square tests to assess group equivalence on home visitor characteristics (demographics, EBP readiness), and client characteristics; those that differ between groups will be included as covariates. We will conduct latent growth curve (LGC) modeling in Mplus to examine the impact of study condition on change over time in primary and secondary outcomes. Mplus provides full information maximum likelihood estimation that produces unbiased parameter estimates under the assumption that the data are missing at random (MAR), and outperforms other missing data approaches even when MAR is not met. Analyses will use a 2 (study condition) X 3 (time) repeated measures intent-to-treat design. First, we will use likelihood ratio difference tests of nested models to determine the overall shape of the individual change trajectories: no change or linear change. Next, we will test unconditional models for all outcomes to obtain the average change effect. Third, we will add study condition to test its impact on initial status and change over time. Model

fit will be evaluated via chi-square, RMSEA, CFI, and TLI, and condition effects will be demonstrated by a statistically significant slope parameter, as tested by the pseudo z test, associated with study condition. For normally distributed outcomes, we will use conventional LGC models, with the appropriate estimator selected based on the distributional properties of the DVs. If client outcomes deviate substantially from normality, we will apply a negative binomial estimator, as recommended for count outcomes (i.e., days of SU) with a distribution that is skewed toward zero. Effect size estimates using Cohen's d will be calculated for all condition effects on client outcomes based on published LGC model recommendations.

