The LGC modeling described above is our preferred approach for analysis. However, given our small sample, we present an alternative analytic strategy in case the longitudinal models fail to converge. If this occurs, we will conduct a series of ANOVAs to test the difference between study conditions on client outcomes separately at each follow-up time point (3- and 6-month), including the baseline value of the outcome as a covariate. Effect sizes will be calculated using Cohen's d .

Exploratory post-hoc analyses using the methods described above will be conducted to examine: (1) condition differences in home visitor-client alliance; and (2) differences in SBI-HV impact based on pregnancy status.

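### The plan does not say that the slope is kept after a no-change result in the pooled shape test, yet a condition effect can be shown only through that slope

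*Combined protocol and SAP*

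**What the plan says.** The paragraph on SBI-HV impacts on client outcomes (DATA ANALYSIS) sets three steps for the latent growth models.

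1. Likelihood-ratio tests of nested models are used to "determine the overall shape of the individual change trajectories: no change or linear change".
2. "Next, we will test unconditional models for all outcomes to obtain the average change effect".
3. Study condition is added as a predictor of both starting level and change.

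Condition is absent until step 3, so the shape test in step 1 is run on the two arms pooled. The criterion for an effect follows: "condition effects will be demonstrated by a statistically significant slope parameter". The next paragraph adds ANOVAs at each follow-up visit: "we present an alternative analytic strategy in case the longitudinal models fail to converge". That is the only stated trigger for them. No sentence says what happens to an outcome for which step 1 selects no change.

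**The concern.** A no-change growth model has an intercept and no slope. If it is the model taken into step 3, condition has no slope to act on and the plan's only criterion for an effect cannot be met. The fallback does not help, because an intercept-only model will ordinarily converge.

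The pretest also asks a different question from the trial's. It responds mainly to average change over both arms, whereas the trial asks whether the arms change differently. It is weakest when one arm improves while the other worsens, and weak when only one arm moves. Both patterns are plausible here: clients are enrolled on use before pregnancy, some are expected to have quit already, and the protocol stresses preventing postpartum relapse.

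Preliminary impact on client outcomes is half of the primary aim, and the plan promises Cohen's d for every condition effect. An outcome left without a slope yields no slope-based estimate.

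**Working it through.** **Inputs from the documents**
- Size: "We will enroll 20 home visitors and 40 clients" (STUDY PURPOSE AND AIMS); the analysis section has "clients (N=40) within home visitors (N=10-20) within sites".
- Arms: about 20 clients each, from the interview-sampling example, "if the overall sample of 20 women in the experimental condition includes 8 pregnant women" (Implementation Data Collection).
- Visits: "Analyses will use a 2 (study condition) X 3 (time) repeated measures intent-to-treat design", that is baseline, 3 and 6 months.

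The plan gives no power, variance, effect size or alpha, so there is no figure of its own to reproduce.

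**Assumptions (not in the documents)**
Two-sided 5% at both steps; baseline SD 1 (intercept variance 0.5, residual variance 0.5); slope variance s = 0, 0.05 or 0.10 per 3-month step; complete data; no clustering; the slope is dropped when no change is selected.

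**Hand check, d=0.5, pretest of the mean slope only (1 df)**
With three equally spaced visits the fitted slope is half the 6-month change, so both tests can be written on that change.
- Variance of the change: v = 4s + 2 x 0.5 = 1.0, 1.2 or 1.4.
- Condition test: SE = sqrt(2v/20) = 0.316, 0.346 or 0.374; z = 0.5/SE = 1.58, 1.44 or 1.34; power about 0.35, 0.30 or 0.27.
- Pretest, control flat: the pooled mean change is d/2 = 0.25 with SE sqrt(v/40) = 0.158, 0.173 or 0.187, so z is again 1.58, 1.44 or 1.34. (This ignores the small inflation of the pooled variance by the arm difference.) The pretest has the same power as the condition test, so no change is chosen in about 65-73% of trials.
- With equal arms the pooled mean and the arm difference are independent, so power after the pretest is about the product: 0.35² = 0.12, 0.30² = 0.09, 0.27² = 0.07.
- Arms moving by d/2 in opposite directions: the pooled change is 0 and the pretest passes about 5%. Power is about 0.05 x 0.35 = 0.018 down to 0.05 x 0.27 = 0.013.
- Both arms also moving 0.5 SD in the direction of benefit: the pooled change is 0.5 + 0.25 = 0.75, z = 0.75/0.158 = 4.7 to 0.75/0.187 = 4.0, and no change is chosen in about 2% or fewer.

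**Simulation, same variances, 3-df test (slope mean, slope variance, covariance), 1,000 runs per setting**

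| True d | Pattern | No change chosen | Power, slope always fitted | Power, slope dropped |
|---|---|---|---|---|
| 0.5 | control flat | 55-78% | 0.23-0.36 (both patterns) | 0.03-0.12 (both patterns) |
| 0.5 | opposite | 72-95% | as above | as above |
| 0.8 | control flat | 29-45% | 0.54-0.71 (both patterns) | 0.38-0.43 |
| 0.8 | opposite | 60-94% | as above | 0.05-0.26 |

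Smaller repeat runs (300-500 per setting) widen the no-change ranges to 51-97% at d=0.5 and 23-95% at d=0.8. They put power at d=0.5 at 0.21-0.37 with the slope always fitted; the formula gives 0.27-0.35, so the low end is simulation error. With both arms also moving 0.5 SD, no change was chosen in under 3%.

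**Second set of assumptions**
Within-person correlation 0.6; slope SD 0 or 0.2 per 3 months; 20,000 runs per setting.
- Control flat, d=0.5: no change in 65-71% (3 df) or 59-62% (1 df); power falls from 0.39-0.46 to 0.13-0.19.
- Control flat, d=0.8: no change in 30-36% or 22-27%; power falls from 0.75-0.82 to 0.53-0.63.
- Opposite, d=0.8: no change in 79-92% or 95-96%; power after the pretest 0.03-0.17.
- Both arms also moving 0.5 SD: no change in under 1%.
- 30 clients (75% follow-up, the low end quoted under RETENTION STRATEGIES), control flat, d=0.8: no change in 43-49% or 35-39%.

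The z test in this second set has type I error of about 0.06-0.07, so its power figures are slightly high.

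**The case against.** The strongest objection is that the gate is inferred. A reader might conclude that the plan leaves real condition effects untested. The documents do not say that. Step 2 covers all outcomes and seeks an average change effect, which presupposes a slope in each. Step 3 tests condition on change without exception. On that reading step 1 only describes shape and nothing is lost. This stands as a limit on the claim. It does not remove the point: a test meant to determine the shape has little purpose if its result is ignored, and the silence leaves the analyst free to keep or drop the slope outcome by outcome after seeing the data.

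Second, the pretest is not wholly blind to condition. The plan speaks of individual trajectories, and in a 3-df test arms that diverge add slope variance. That is correct, but with 40 clients the test has little power to see it: at d=0.8 with opposite movement it still chose no change in 60-94% of runs.

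Third, the loss depends on the scenario. Common change in both arms is also plausible, since the protocol describes heightened motivation in this period, and then the pretest almost always keeps the slope. This stands.

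A reader might also infer that an ordinary, unscaled likelihood-ratio difference would be used beside the sandwich variance, which would make its reference distribution wrong. The plan does not say so, and it leaves the choice of estimator open, so that criticism is not made here.

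**Conclusion.** The point holds as an unspecified branch with a real but conditional cost. The plan pretests shape without condition, recognises an effect only through the slope, and has no rule for an outcome judged unchanging. If the selected shape is carried forward, that outcome cannot show a condition effect.

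The cost is large when average change is small: at d=0.5 with control flat or the arms diverging, most of an already low power is lost (about 0.2-0.4 down to 0.01-0.13 under the first set of variances). It is negligible when both arms change by around half an SD. All figures rest on assumed variances and ignore clustering by home visitor; incomplete follow-up enters only through the 30-client case. The abstinence and days-of-use outcomes were not simulated.

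Severity is below must-fix. This is a 40-client pilot, and the opening note reports that randomization was dropped, 14 participants were enrolled and the longitudinal analyses were not carried out. The point matters for the plan as written and for any later trial that reuses it.

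**What to change.** State that the linear slope and the condition-by-time term are fitted for every outcome, whatever the shape test shows. If the slope variance cannot be estimated, fix it at zero and keep the fixed condition-by-time effect. Keep the comparison of no-change and linear models as description only, with no bearing on whether condition is tested or an effect size reported.

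The cost is a few sentences of SAP wording. It needs no new data, and it avoids the power loss shown above.

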Prior to SBI-HV training, home visitors in both conditions will complete a brief demographic survey. They will also complete the *Evidence-Based Practice Attitude Scale*, a 15-item measure of provider attitudes towards evidence based practices (EPBs), that generates 4 scales: Appeal of EBPs, Required Use by Organization, Openness to Trying EBPs, Unfavorable Attitudes toward EBPs. Consistent factor structure and good internal consistency have been shown in diverse provider samples. Home visitors will complete 1-2 item brief fidelity checklists after each visit in which a facilitation protocol is intended to be implemented. These items will be sent to home visitors via text message and they will respond via text message.

Client Measures

Clients will complete a battery of assessments at baseline, 3-month, and 6-month follow-up using instruments that have demonstrated strong psychometric properties in similar samples. At baseline, we will administer selected sections of the *Addiction Severity Index (ASI)* to assess basic demographics and lifetime and current problems with physical health, employment and finances, illegal activity, family relationships, and psychiatric symptoms. Trauma history will be assessed at baseline via the *Childhood Trauma Questionnaire-Short Form*. Primary study outcomes (to be assessed at baseline, 3-mo, and 6-mo follow-up) include substance use, depression, and parenting stress. Substance use will be assessed via the *Timeline Follow Back Interview*, a calendar-based method for assessing quantity and frequency of SU. Primary SU outcomes will include seven-day point-prevalence abstinence rates and monthly reported days of use. Depression will be assessed via the *Beck Depression Inventory-II*, a 21-item scale measuring depressive symptoms that is widely used in research and practice with perinatal women. Parenting stress will be assessed using the *Parenting Stress Index-Short Form*, a 36-

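### A 40-client pilot aimed at preliminary impacts treats a significant slope as demonstrating an effect, outcome by outcome, with four primary outcomes and no stated alpha, hierarchy, multiplicity control or power basis

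*Combined protocol and SAP*

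**What the plan says.** Under Data Analysis (SBI-HV Impacts on Client Outcomes), latent growth curve models are planned for the primary and secondary outcomes. The criterion is that "condition effects will be demonstrated by a statistically significant slope parameter, as tested by the pseudo z test, associated with study condition". Cohen's d is to be calculated for all condition effects.

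Under Study Measures (Client Measures), the primary outcomes "include substance use, depression, and parenting stress". Substance use is then split: "Primary SU outcomes will include seven-day point-prevalence abstinence rates and monthly reported days of use". With depression and parenting stress, that makes four primary outcomes.

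If the growth models fail to converge, the fallback is a set of baseline-adjusted ANOVAs run "separately at each follow-up time point (3- and 6-month"), again with Cohen's d.

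On size, Study Purpose and Aims says "We will enroll 20 home visitors and 40 clients". The analysis section describes "clients (N=40) within home visitors (N=10-20) within sites". The same aims section describes the effect objective as determining preliminary impacts, beside feasibility, acceptability and fidelity.

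No significance level, sidedness, ordering of the primary outcomes, multiplicity rule, power calculation or sample-size rationale appears. Only the alliance and pregnancy-status analyses are labelled exploratory.

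**The concern.** The aims promise preliminary evidence, but the analysis section uses a confirmatory criterion. Followed as written, one significant slope among the four primaries could be reported as a demonstrated effect, although nothing limits the chance that it is a false positive. A non-significant slope could be read as no effect, although the sample cannot exclude a moderate one. Either reading would mislead a decision on whether, and for which outcome, to run a larger trial.

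**Working it through.** **Inputs from the document.** There are 40 clients and four primary outcomes. The allocation ratio is not stated, but a worked example in Implementation Data Collection ("if the overall sample of 20 women in the experimental condition includes 8 pregnant women") implies 20 per arm. Home visitors number 10–20, so there are about 2–4 clients each. Follow-up in earlier studies ran from 75% to over 95% (Retention Strategies).

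**Assumptions.** Alpha is two-sided 5% per test, because none is stated. Illustrative true effects are d = 0.5 and 0.8. Between-outcome correlation is 0 to 0.7, baseline-to-follow-up correlation 0.5–0.7 and ICC 0 to 0.10. The document gives none of these. It also gives no power figure, so N = 40 can be neither reproduced nor called wrong.

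**1. False claims over the four primaries, all nulls true**
- Independent outcomes: 1 − 0.95⁴ = 1 − 0.8145 = 18.5%.
- Equally correlated normal outcomes (simulation): 17.4% at 0.3, 15.6% at 0.5 and 13.0% at 0.7.
- Fallback, 4 outcomes × 2 time points = 8 tests: 1 − 0.95⁸ = 33.7% if independent. This is an upper figure, because the two time points of one outcome are correlated. With assumed correlations of 0.5–0.7 within and 0.3–0.5 between outcomes, simulation gives 25–30%.

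These figures assume that each test holds its 5% level. The plan names a sandwich variance and a z test and mentions no small-sample correction. In a simplified null simulation (one measurement per client, not the growth model), an uncorrected version rejected about 8% of the time with 20 home visitors and 12% with 10.

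**2. Power for one outcome, 20 per arm, no clustering, no dropout**

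A comparison at one time point stands in for the slope test.
- Unadjusted: noncentrality = d√(n/2) = 0.5 × √10 = 1.58, with 38 df and critical t = 2.024. Power is 34%. At d = 0.8 it is 69%.
- Baseline-adjusted: replace d by d/√(1 − r²). For d = 0.5 this is 0.5/0.866 = 0.577 at r = 0.5 and 0.5/0.714 = 0.700 at r = 0.7. With 37 df, power is 43% and 58%. At d = 0.8 it is 81% and 93%.
- Unfavourable case, unadjusted: 10 home visitors, 75% follow-up and ICC 0.10 leave 15 clients per arm, 3 per home visitor. The design effect is 1 + 2 × 0.10 = 1.2 and the effective n is 15/1.2 = 12.5 per arm. By the normal approximation, power at d = 0.5 is Φ(0.5 × √6.25 − 1.96) = Φ(−0.71) = 24%.

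**3. Precision**

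At 20 per arm, unadjusted and unclustered, the 95% interval half-width is about 2.024 × √(2/20) = 0.64 SD. An observed difference of zero would still be compatible with a d of about 0.6 in either direction.

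**The case against.** The strongest reply is that this is a pilot that says so. It admits its small sample, provides for non-convergence and plans effect sizes throughout, so one verb is being made to carry too much. That reply limits the point in several ways. A reader might infer more than the document supports:

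- **That false claims are likely.** For the four primaries the risk is 13–18.5%, and only if all four nulls hold. That is roughly three to four times nominal, but well below even odds. Counting every secondary outcome at two time points would raise it, but that count is not secure. Treatment engagement is described in one place as measured only at 6 months, alliance is labelled exploratory, and repeated measures are correlated.
- **That any one of four makes the trial positive.** No such rule is stated. The criterion applies to each outcome separately and also covers secondary outcomes.
- **That true effects are mostly missed.** This depends on an assumed effect size and on the model. The planned analyses use baseline information, which takes power at d = 0.5 to 43–58% before clustering and dropout, and power at d = 0.8 is higher still.
- **That only inflated, significant effects will be kept.** Cohen's d is planned for all condition effects, and in the fallback with no significance condition. The document does not clearly impose a significance filter.

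The opening note also says that randomisation was eliminated, with 14 enrolled and 4 of them in control, and that the longitudinal analyses could not be carried out. No reported result is at issue.

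What survives is that the criterion is written, the four primaries are not labelled exploratory, and the pilot's purpose is a reason against using significance as the test of an effect.

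**Conclusion.** The point holds as a defect in the plan's decision rule. The wording is confirmatory where the aim is preliminary, and nothing controls or calibrates the error rates of the four primary tests. At an assumed two-sided 5% per test, the chance of at least one false primary claim is 18.5% under independence, or 13–17% at correlations of 0.7–0.3. Power per outcome at d = 0.5 is about 34% unadjusted or 43–58% baseline-adjusted, at 20 per arm before clustering and dropout. The sizes rest on an alpha, effect sizes and correlations that the document does not give. The inconsistency between aim and criterion does not depend on them. It should be corrected in the plan as written and not carried into a later trial.

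**What to change.** Replace the criterion sentence under Data Analysis with: *Condition effects will be reported for every outcome, whatever the p-value, as estimates (including Cohen's d) with 95% confidence intervals that account for the randomised home visitors; no effect will be called demonstrated on a p-value in this pilot.* Apply the same wording to the fallback ANOVAs.

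A multiplicity adjustment is not needed for this fix and would be a debatable trade-off in a pilot. By the normal approximation, Bonferroni over four outcomes (0.05/4 = 0.0125 each) would cut unadjusted power at d = 0.5 and 20 per arm from 35% to 18%.

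The change is one of wording, and Cohen's d is already planned. The downside is that the pilot can claim less.

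### The fallback ANOVAs state no adjustment for clustering by home visitor, the randomised unit, and the plan's plain sandwich estimator would not hold a 5% level with 10–20 clusters

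*Combined protocol and SAP*

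**What the plan says.** Under Study Purpose and Aims: "The pilot RCT will be a cluster-randomized trial, with home visitors randomly assigned to study condition", and "We will enroll 20 home visitors and 40 clients".

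Data Analysis, under SBI-HV Impacts on Client Outcomes, describes the structure as "clients (N=40) within home visitors (N=10-20) within sites". It says that random effects would be unstable and then that "we will use the sandwich variance estimator to adjust standard errors as appropriate to account for nesting of clients within home visitors". It adds: "Site will be included as a fixed covariate in all models". Latent growth curve modelling is introduced only after these sentences.

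The closing part of Data Analysis turns to the fallback: "we present an alternative analytic strategy in case the longitudinal models fail to converge". In that event "we will conduct a series of ANOVAs to test the difference between study conditions on client outcomes separately at each follow-up time point" (3 and 6 months), "including the baseline value of the outcome as a covariate", with Cohen's d. This paragraph neither repeats nor withdraws the clustering adjustment.

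No significance level, ICC or number of sites is given. The note at the front of the document reports that randomisation was eliminated, that 14 clients were enrolled (4 control, 10 intervention), and that the planned longitudinal analyses could not be carried out. It does not say whether the fallback was used.

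**The concern.** Clients of one home visitor share that person's skill, caseload and delivery of the facilitation scripts, so their outcomes may be correlated. Because condition is assigned to the home visitor, the whole of that correlation enters the variance of the treatment contrast. A standard ANOVA takes its error term from the spread between clients and counts 40 independent observations.

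The fallback is there because the sample is small, so it is more than a remote contingency. It would be applied to several primary outcomes at two time points. Intervals that are too short would make the preliminary impacts look firmer than the data allow.

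**Working it through.** The plan has no sample-size or error-rate figure to reproduce, so the check asks what error rate each reading of the fallback would have.

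**Inputs from the plan.** 40 clients; 20 home visitors (Study Purpose and Aims) or as few as 10 (Data Analysis). Clients per home visitor: m = 40/20 = 2 or 40/10 = 4.

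**Assumptions.** Two-sided 5% level; ICC 0.01–0.20, taken after baseline adjustment; equal arms, equal clusters, full follow-up; no site effect. The simulations use a baseline–outcome correlation of 0.5.

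**Reading 1: unadjusted client-level ANOVA with baseline covariate.**

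Design effect DE = 1 + (m − 1) × ICC. The unadjusted standard error is 1/√DE of the correct one. Type I error ≈ 2 × [1 − Φ(1.96/√DE)].

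Example, m = 4 and ICC 0.20: DE = 1 + 3 × 0.20 = 1.60; 1/√1.60 = 0.791; 2 × [1 − Φ(1.96 × 0.791)] = 12.1%.

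| Home visitors × clients | ICC | DE | SE as share of correct | Type I error, formula | Simulated (20,000 null trials) |
|---|---|---|---|---|---|
| 20 × 2 | 0.01 | 1.01 | 99.5% | 5.1% | 5.1% |
| 20 × 2 | 0.05 | 1.05 | 97.6% | 5.6% | 5.3% |
| 20 × 2 | 0.10 | 1.10 | 95.3% | 6.2% | 6.1% |
| 20 × 2 | 0.20 | 1.20 | 91.3% | 7.4% | 7.5% |
| 10 × 4 | 0.01 | 1.03 | 98.5% | 5.4% | 5.6% |
| 10 × 4 | 0.05 | 1.15 | 93.3% | 6.8% | 6.6% |
| 10 × 4 | 0.10 | 1.30 | 87.7% | 8.6% | 8.3% |
| 10 × 4 | 0.20 | 1.60 | 79.1% | 12.1% | 12.0% |

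At ICC 0 the test is correct. Nothing in the plan fixes the number of clients per home visitor. With one assumed pattern of unequal clusters, ICC 0.05–0.20 gave about 6.8–11.5% (20 home visitors) and 7.6–17.0% (10).

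**Reading 2: the plain sandwich estimator carries over, with a normal reference.** Simulated type I error over ICC 0–0.20 with equal clusters was 8.1–8.6% with 20 home visitors and 12.2–12.7% with 10. The excess is there even at ICC 0, because the uncorrected sandwich is biased downwards when clusters are few.

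**Alternatives, equal clusters.**

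- t-test on baseline-adjusted home-visitor means: between 4.6% and 6.6% across several simulation runs. The runs differ in length and may differ in how the baseline slope is estimated.
- Sandwich with a simple small-sample factor and a t reference on (home visitors − 2) df: 5.1–5.5% with 20 and 5.8–6.3% with 10. With the unequal clusters above it stayed at about 9–12%, so a simple factor is not enough if client numbers are uneven.

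Not simulated: the bias-reduced variance (CR2) with Satterthwaite df, home-visitor means with unequal clusters, and site terms.

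**Cost in interval width.** Relative to the unadjusted interval, the factor is √DE × t(home visitors − 2)/t(37), with t(37) = 2.026, t(18) = 2.101 and t(8) = 2.306.

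- 20 home visitors: ICC 0.05, 1.025 × 1.037 = 1.06; ICC 0.20, 1.095 × 1.037 = 1.14.
- 10 home visitors: ICC 0.05, 1.072 × 1.138 = 1.22; ICC 0.20, 1.265 × 1.138 = 1.44.

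**The case against.** A reader might infer that the fallback is an ordinary ANOVA, that its error rate therefore exceeds 5%, and that only the growth model is protected. The documents do not support that reading.

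- The sandwich sentence stands under the general heading on client outcomes, before any model is named, and is not tied to the growth model. It can be taken to cover the fallback. There are signs the other way: site is to enter all models while the sandwich applies only as appropriate, and the fallback paragraph restates Cohen's d but not clustering. These signs do not settle it. What is shown is a missing statement.
- The excess depends on an ICC and a level that the plan does not give. At the planned 2 clients per home visitor and ICC 0.01–0.05 it is under one percentage point. The larger figures need the 10-home-visitor end of the range, a higher ICC, or uneven clusters.
- The contrast between a protected main analysis and an unprotected fallback fails. In the equal-cluster settings the plain sandwich does worse than the unadjusted ANOVA.

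All of this stands. It does not remove the point, because on either reading the fallback lacks a method suited to 10–20 clusters. It is also fair that this is a pilot seeking preliminary impacts and that the trial was not completed as randomised. That lowers the weight of the point.

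**Conclusion.** The concern holds in conditional form. The fallback paragraph does not say how clustering by home visitor is handled, and both available readings miss the nominal level. The sizes rest on an assumed two-sided 5% level, ICC up to 0.20, equal clusters, full follow-up and no site effect. Uneven client numbers would make them larger.

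Severity is low to moderate. With randomisation eliminated and 14 clients enrolled, the planned comparison was not carried through, and a corrected standard error does not restore randomisation. The point still applies to any between-condition ANOVA that is reported.

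**What to change.** In the fallback paragraph of Data Analysis, replace the ANOVAs with one of the following, and state the significance level:

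1. A baseline-adjusted comparison of home-visitor means, using a t reference with df equal to the number of home visitors minus the number of fitted cluster-level parameters. Intercept and condition alone leave (home visitors − 2). S sites entered as fixed terms remove a further (S − 1), and a home-visitor-level baseline covariate removes one more.
2. A client-level baseline-adjusted model with a small-sample-corrected cluster-robust variance, such as CR2, and Satterthwaite df. This suits uneven client numbers better in principle, but its error rate should be checked by simulation at the cluster sizes actually obtained.

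Say also whether site stays in the fallback model. With 10 home visitors, site terms could use up much of the df.

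The work is a few sentences and a few lines of code. The statistical price is wider intervals: on the figures above about 6–14% with 20 home visitors and 22–44% with 10 for ICC 0.05–0.20, and more once site terms take df. If no between-condition ANOVA is to be reported from the 14 clients, a sentence saying so is enough.
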